- HIV-RNA Cepheid test at baseline, Week 24, Week 48, Week 72, Week 96 and reinduction
- Plasma will be stored at each visit for future use to evaluate use of alternate HIV assays and cabotegravir PK. Small hair samples will be stored at visit weeks 8, 24, 32, and 48 to assess cabotegravir PK.
- Participants that stop CAB-LA prior to the end of the extension time period will continue to be followed in the study but *not* be actively followed beyond the 96 week followup time of the study.
 - Oral PrEP (TDF/3TC) will be recommended to cover tail
 - Participants will switch back to Q12 week follow-up

Table 5. Schedule of Evaluations Dynamic Choice Prevention Extension – Baseline to Week 48

	Screening/ Baseline	Week 12	Week 24	Week 36	Week 48 ⁴
DCP Intervention (For persons not receiving CAB-LA)¹					
Study visit	X	X	X	X	X
DCP intervention, including:	X	X	X	X	X
- Offer PrEP, PEP, prevention options ²	X	X	X	X	X
- HIV testing options	X	X	X	X	X
- Visit location choice	X	X	X	X	X
- Structured assessment of barriers	X	X	X	X	X
- GBV screening	X		X		X
HIV self-test (alternative to rapid)		X	X	X	
Rapid (blood-based) HIV test	X	X	X	X	X
STI symptom screen	X	X	X	X	X
Pregnancy testing (optional)	X	X	X	X	X
DCP (including those persons on CAB-LA) and SOC					
Measure height (baseline only) and weight	X		X		X
Assess self-reported PrEP/PEP use and HIV risk over prior 6 months	X		X		X
Complete Week 24 or 48 Visit eCRF			X		X
Hair sample collection if any PrEP or PEP doses taken in last 30 days			X		X
HIV RNA			X		X
SOC Only					
Study Visit	X		X		X
Referral to standard prevention options	X		X		X
Rapid (blood-based) HIV test	X		X		X
Suspected seroconversion³					

¹Late visits for routine assessments will not be considered Protocol Violations, allowing flexibility during the COVID-19 pandemic

²This assessment will be done on all intervention participants at baseline

³See Figure 2

⁴Week 48 visits may occur between 40 and 56 weeks after Baseline

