If CAB-LA is not available in country at the 48-week endpoint, all participants in the intervention arm will have the opportunity to continue on the study until week 96 or until CAB-LA is available in country, whichever occurs first, according to the schedules of evaluation described in Tables 5a and 6. Participants who are currently on CAB-LA at the Week 48 visit may continue on CAB-LA through Week 96. CAB-LA may not be initiated or restarted during the additional 48 week extension to Week 96. Prior to conducting procedures for visits after Week 48, participants in the intervention arm will be reconsented to extend their participation up to Week 96.

Table 5a. Schedule of Evaluations for Extension of Intervention Arm – Week 60 to Week 96

	Week 60	Week 72	Week 84	Week 96 ³
DCP Intervention (For persons not receiving CAB-LA)¹				
Study visit	X	X	X	X
DCP intervention, including:	X	X	X	X
- Offer PrEP, PEP, prevention options ^{2,*}	X	X	X	X
- HIV testing options	X	X	X	X
- Visit location choice	X	X	X	X
- Structured assessment of barriers	X	X	X	X
- GBV screening		X		X
HIV self-test (alternative to rapid)	X	X	X	
Rapid (blood-based) HIV test	X	X	X	X
STI symptom screen	X	X	X	X
Pregnancy testing (optional)	X	X	X	X
Measure weight		X		X
Assess self-reported PrEP/PEP use and HIV risk over prior 6 months		X		X
Complete Week 72 or 96 Visit eCRF		X		X
HIV RNA		X		X
Suspected seroconversion²				

¹Late visits for routine assessments will not be considered Protocol Violations, allowing flexibility during the COVID-19 pandemic or for other outbreaks.

²See Figure 2

³Week 96 visits may occur between 88 and 104 weeks after Baseline

*Participants will not be given the option to initiate or restart CAB-LA after the Week 48 visit; only other prevention options will be available.

Table 6. Schedule of Evaluations for CAB-LA users (weeks indexed by date of initial CAB LA injection) – Baseline to Week 96

	CAB Screening/ Baseline	CAB Week 4	CAB Week 8	CAB Week 16	CAB Week 24	CAB Week 32	CAB Week 40	CAB Week 48 ⁷	CAB Week 56	CAB Week 64	CAB Week 72	CAB Week 80	CAB Week 88	CAB Week 96 ⁷
Measure weight	X				X			X			X			X
CAB LA injection	X	X	X	X	X	X	X	X	X	X	X	X	X	
STI Symptom Screen	X	X	X	X	X	X	X	X	X	X	X	X	X	X
Suspected Seroconversion	X	X	X	X	X	X	X	X	X	X	X	X	X	X
HIV Testing														
-Rapid test (Country std. algorithm)	X	X	X	X	X	X	X	X	X	X	X	X	X	X
-HIV RNA ⁶	X				X			X			X			X
-Stored plasma (2cc) for future HIV testing	X	X	X	X	X	X	X	X	X	X	X	X	X	X
CAB PK														

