-Hair sample (if CAB-LA received in last 120 days)			X		X	X		X						
-Stored plasma (from 2 cc sample above)		X	X	X	X	X	X	X						
Safety Labs														
-Pregnancy testing ¹	X	X	X	X	X	X	X	X	X	X	X	X	X	X
-ALT Monitoring ^{4, 5}	X		X*		X			X*			X*			X*
Adverse Event Monitoring	X	X	X	X	X	X	X	X	X	X	X	X	X	X
GBV Screening	X				X			X			X			X
Survey and IDI														
-Participant CAB-LA Survey and IDI ²	X				X			X						
-Provider and Clinic Staff DCP-LA Survey and IDI	X				X			X						
Costing³	X	X				X								
For participants who stop CAB LA before end of extension study														
-For 48 weeks from last injection: Recommend oral PrEP (TDF/3TC) to cover tail														
-Switch back to Q12 week visits - HIV RNA and pregnancy testing Q12 weeks														

¹For women who become pregnant, repeat pregnancy tests are not needed. Women who become pregnant during the study will be followed to delivery for assessment of mother and infant status

²Participant survey/IDI will be conducted at start of CAB-LA and Weeks 24 and 48 from time of CAB-LA start or discontinuation.

³Costing will occur between weeks 24-48.

⁴ALT Monitoring will occur at baseline, Week 24 for all participants. *Per provider discretion, ALT monitoring will occur at Weeks 8, 48, 72 and 96.

⁵Bilirubin and additional labs indicated will be tested in the case of ALT increase.

⁶HIV RNA will be drawn at CAB-LA reinduction, as described in Table 6.

⁷ Week 48 visits may occur between 40 and 56 weeks after Baseline; Week 96 visits may occur between 88 and 104 weeks after Baseline; only participants on CAB-LA at the Week 48 visit may take CAB-LA between weeks 48 and 96.

E. Extension Consent Process

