- a. The study sponsor, UCSF, will receive CAB-LA directly from ViiV Healthcare and distribute to the country pharmacies per country study drug shipping procedures
- b. In-country pharmacists will receive and log the CAB-LA per country procedure and detailed in the CAB-LA Pharmacy SOPs
- c. As described in 6c below, CAB-LA will be stored at 2°C to 30°C (36°F to 86F) at clinic sites; proper storage and handling will be monitored by in-country pharmacy teams and validated by accountability logs and other source

documents

- d. Details on these procedures are outlined in the Standard Operating Procedures.
 - i. CABPHARM-01 Study Drug Ordering and Acquisition
 - ii. CABPHARM-02 Study Drug Accountability
 - iii. CABPHARM-03 Study Drug Storage
 - iv. CABPHARM-04 Dispensing and Administration of Study Drug
 - v. CABPHARM-05 Disposition and Destruction of Study Drug
 - vi. CABPHARM-06 Communication and Dissemination of Information to the Study Pharmacist

6. Injection Dosing

- a. The initial injection dose of CAB-LA is a single 600-mg (3-mL) intramuscular injection of CAB-LA given 4-weeks apart for 2 consecutive times
- b. After the 2 initiation injection doses given consecutively 4-weeks apart, the continuation injection dose of CAB-LA will be a single 600-mg (3-mL) intramuscular injection of CAB-LA, every 8-weeks.
- c. There is a +/- 7 day window for before or after the date the participant is scheduled to receive their next injection

7. **Missed Doses.** Study staff will provide adherence support to CAB-LA participants. When doses are missed, study staff will follow the applicable guidelines. Providers will work pro-actively and prospectively identify periods during which participants are likely to miss doses (eg travel). Participants will be provided with oral bridging prevention medication (TDF-FTC) to cover these periods. Upon return to clinic for planned or unplanned missed doses, CAB-LA dosing will be as per protocol below.

- a. If a scheduled injection visit is missed or delayed by more than 7 days, the study clinician will determine when resumption is appropriate.
- b. Recommended Dosing after a missed visit is detailed in **Table 7**.

Table 7. Missed Dosage Recommendations

Time since Last Injection	Recommendation
If second injection is missed and time since first injection is:	

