Less than or equal to 8-weeks	Administer 600-mg (3-mL) gluteal intramuscular injection of CAB-LA as soon as possible, then continue to follow the every 8-weeks injection dosing schedule.
Greater than 8-weeks	Restart with 600-mg (3-mL) gluteal intramuscular injection of CAB-LA, followed by a second 600-mg (3-mL) initiation injection 4-weeks later. Then continue to follow the every 8-weeks injection dosing schedule thereafter.

If third or subsequent injection is missed and time since prior injection is:	
Less than or equal to 12 weeks	Administer 600-mg (3-mL) intramuscular injection of CAB-LA as soon as possible, then continue with the every 8-weeks injection dosing schedule.
Greater than 12-weeks	Restart with 600-mg (3-mL) gluteal intramuscular injection of CAB-LA, followed by the second 600-mg (3-mL) initiation injection dose 4-weeks later. Then continue with the every 8-weeks injection dosing schedule thereafter.

4. Contraindications. CAB-LA is contraindicated in individuals:

- a. With unknown or positive HIV-1 status
- b. With previous hypersensitivity reaction to cabotegravir
- c. Receiving the following co-administered drugs for which significant decreases in cabotegravir plasma concentrations may occur due to uridine diphosphate glucuronosyltransferase:
 - i. Anticonvulsants: Carbamazepine, oxcarbazepine, phenobarbital, phenytoin
 - ii. Antimycobacterials: Rifampin, rifapentine

5. Drug Interactions

- i. **Use of Other Antiretroviral Drugs after Discontinuation of CAB-LA.** Residual concentrations of cabotegravir may remain in the systemic circulation of individuals for prolonged periods (up to 12 months or longer). These residual concentrations are not expected to affect the exposures of antiretroviral drugs that are initiated after discontinuation of CAB-LA
- ii. **Potential for Other Drugs to Affect CAB-LA.** Cabotegravir is primarily metabolized by UGT1A1 with some contribution from UGT1A9. Drugs that are strong inducers of UGT1A1 or 1A9 are expected to decrease cabotegravir plasma concentrations; therefore, coadministration of CAB-LA with these drugs is contraindicated
- iii. **Established and Other Potentially Significant Drug Interactions.** Information regarding potential drug interactions with cabotegravir is provided in **Table 8** below.

Table 8. Drug Interactions with CAB-LA

Concomitant Drug Class: Drug Name	Effect on Concentration	Clinical Comment

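### Appendix 18 gives two incompatible CAB-LA injection calendars: the third dose is due at week 12 under Section F item 6 and at week 8 under Table 6

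*Protocol*

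**What the plan says.** All references are to Protocol Appendix 18.

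- **Section F, item 6a:** the initial dose is a single 600-mg "injection of CAB-LA given 4-weeks apart for 2 consecutive times".
- **Item 6b:** after those two doses, "the continuation injection dose of CAB-LA will be a single 600-mg (3-mL) intramuscular injection of CAB-LA, every 8-weeks".
- **Item 6c:** "There is a +/- 7 day window for before or after the date the participant is scheduled to receive their next injection".
- **Item 7a:** "If a scheduled injection visit is missed or delayed by more than 7 days, the study clinician will determine when resumption is appropriate".
- **Table 7:** a participant who must restart after missing the second dose gets one injection, "followed by a second 600-mg (3-mL) initiation injection 4-weeks later. Then continue to follow the every 8-weeks injection dosing schedule thereafter". The restart row for a third or later dose follows the same pattern. A third or later dose needs no restart up to 12 weeks after the one before it.
- **Table 6**, titled "Schedule of Evaluations for CAB-LA users (weeks indexed by date of initial CAB LA injection"): the injection row is marked at baseline and weeks 4, 8, 16, 24, 32, 40, 48, 56, 64, 72, 80 and 88. There is no week-12 column. The row "Hair sample (if CAB-LA received in last 120 days") is marked at weeks 8, 24, 32 and 48.
- **Section D** repeats those weeks: "Small hair samples will be stored at visit weeks 8, 24, 32, and 48 to assess cabotegravir PK". Section H repeats them too. It ties plasma to each injection and takes hair to be collected before injections.
- **Sections D and E** describe four-weekly injection visits in the first two months and eight-weekly visits after that.

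**The concern.** A clinician following Section F and one following Table 6 would give the third injection, and every later one, on different dates. No legible text says which governs. Three things depend on the answer:

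1. Which third doses are more than 7 days late and so go to the clinician under item 7a.
2. The Table 4 (RE-AIM) fidelity measure, which counts providers offering CAB-LA on the right schedule. From dose 3 onward it has no single reference.
3. The Section H hair-plasma correlation at the end of the dosing interval. It needs hair taken just before an injection, yet hair is tied to fixed weeks while plasma follows the injections.

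**Working it through.** No sample-size formula applies; this is calendar arithmetic. Week 12 is derived from item 6, not printed there.

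**1. Item 6 calendar.** Dose 1 at week 0, dose 2 at week 4, dose 3 at 4 + 8 = week 12, then every 8 weeks: 0, 4, 12, 20, 28, 36, 44, 52, 60, 68, 76, 84, 92 (13 dates to week 96).

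**2. Table 6 calendar.** Thirteen marks under 14 columns (0, 4, 8, 16, 24 and so on to 96), with week 96 blank: 0, 4, 8, 16, 24, 32, 40, 48, 56, 64, 72, 80, 88.

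**3. Could a broken table explain it?** No. There is no week-12 column, so no position of the single blank yields 0, 4, 12. Moving the blank to week 8 would give 0, 4, 16. The hair marks fall on the weeks that Sections D and H state independently, so the columns are aligned.

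**4. What Table 7 implies.** The no-restart limit for dose 2 is 8 weeks after dose 1, when dose 2 is due at 4: a grace of 8 - 4 = 4 weeks. For dose 3 the limit is 12 weeks after dose 2. The grace is 12 - 8 = 4 weeks under item 6, but 12 - 4 = 8 weeks under Table 6. Table 7 therefore fits item 6.

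**5. Dose 3 window, in days after dose 2, with the 7-day tolerance.**

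| Rule | Due | On time |
|---|---|---|
| Item 6 | 56 | 49 to 63 |
| Table 6 | 28 | 21 to 35 |

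The windows share no day, and days 36 to 48 fall in neither. A dose on days 49 to 63 is on time under item 6 and late under Table 6. A dose on days 21 to 35 is on time under Table 6 and early under item 6.

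**6. Later doses.** Only weeks 0 and 4 are common. The other 11 item 6 dates are each 4 weeks from the nearest nominal Table 6 visit. Footnote 7 of Table 6 allows week-48 visits at weeks 40 to 56 and week-96 visits at weeks 88 to 104. Three of the 11 (weeks 44, 52 and 92) fall inside those windows, and 11 - 3 = 8 do not.

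**7. Hair timing.** Weeks since the previous dose at hair weeks 8, 24, 32 and 48:
- Table 6: 4, 8, 8, 8, each an injection date.
- Item 6: 8 - 4, 24 - 20, 32 - 28 and 48 - 44, which is 4 each time and halfway through an 8-week interval. No nominal hair week is an injection date, though footnote 7 lets the week-48 sample be taken at the week-44 or week-52 injection.

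**8. Covered time.** Under Section C (Outcomes), coverage lasts 2 months plus 7 days after the last injection: 59 + 7 = 66 to 62 + 7 = 69 days. The longest scheduled gap is 56 days on both calendars, and 56 + 7 = 63 at the end of the window. Neither leaves a gap.

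**9. Number of doses.** Before week 48, 7 on each calendar. Counting week 48 itself, 7 under item 6 and 8 under Table 6.

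**The case against.** Much of the opposing case stands, and it limits the consequences.

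- **Visits follow injections.** Sections D and E align CAB-LA users' visits with their injections, so a site dosing by item 6 might well move the hair samples too. The PK problem needs a hybrid: item 6 dosing with Table 6 hair weeks. It must be stated as conditional, and it touches an exploratory analysis.
- **No restart is triggered.** A dose on the item 6 date comes 8 weeks after dose 2, within the 12-week limit of Table 7. If Table 6 governs and that dose counts as late, the result is a clinician decision under item 7a and no more.
- **The fidelity measure is descriptive.** No hypothesis test rests on it.
- **Sections D and E lean one way.** Four-weekly visits over two months most naturally means weeks 0, 4 and 8, as in Table 6. They could mean doses at 0 and 4 only, so they do not settle the matter, but they show that the conflict is more than one stray cell.
- **Unseen sources.** SOP CABPHARM-04 and Figure 3 may already fix site practice. The appendix would still contradict itself.

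A reader might infer that participants are left unprotected or that the primary endpoint is distorted. Step 8 shows otherwise for on-schedule dosing. Nor do the documents support a claim of safety harm, or that sites are dosing wrongly.

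**Conclusion.** The conflict is real and should be corrected. Appendix 18 places the third injection 56 days after the second in one place and 28 days after it in another. The 7-day windows do not meet, and the calendars stay 4 weeks apart from there on. Confidence is high for the text and limited for any effect at sites.

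What is left undefined is the set of delayed third doses and the reference for the fidelity measure. The PK effect arises only if sites dose by item 6 and keep the nominal hair weeks; then none of the four is a pre-injection date, unless the week-48 window is used. It would be wrong to read this as invalidating the PK analysis.

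Injection-linked HIV tests and plasma samples move with the injections (item 4d and Section H). The HIV RNA and ALT checks that Table 6 sets at fixed weeks do not move automatically.

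**What to change.** With clinical sign-off, state one calendar and align every place that depends on it.

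- **If item 6 governs:** re-time the Table 6 injection visits to weeks 12, 20, 28 and so on. Move the hair weeks in Section D, Table 6 and Section H to injection visits. Reword Sections D and E. Say whether the fixed-week HIV RNA and ALT checks move or remain as separate visits. Update the visit schedule that participants are told before consenting.
- **If Table 6 governs:** amend items 6a and 6b and the Table 7 restart wording to three 4-weekly doses before the 8-week interval. Check whether the 12-week limit still suits a missed third dose.
- **In either case:** define both schedule adherence for the fidelity measure and the end of the dosing interval by actual days since the last injection, from the dispensing logs, and not by nominal week.

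The cost is a protocol amendment and, if the schedule given to participants changes, possible ethics review. The dispensing logs are already a planned data source, so these definitions need no new data collection, and the primary endpoint is unchanged. If CABPHARM-04 or Figure 3 already settles practice, the amendment only has to bring the appendix into line.
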